16.4 Sample Size Determination

This study requires 100 evaluable women for the primary endpoint analysis (50 evaluable patients per arm).

Ninety-two percent of expected patients completed a 3-year assessment of cosmesis in the randomized phase III study reported by Olivotto et al.⁶¹ Expected was defined as patients who were projected to have had their 3-year follow-up visit based on the date of random assignment and who did not experience recurrence, undergo mastectomy, or die. Therefore to be conservative we will anticipate enrolling 10 (5 per arm) additional patients to account for ineligibility, cancellation, major treatment violations, or other reasons. The maximum projected enrollment is therefore 110 women.

In a large randomized controlled trial Whelan and colleagues compared cosmetic outcomes between conventional and hypofractionated whole breast radiotherapy after lumpectomy. At baseline, 84% of patients in the hypofractionated arm were rated as having good or excellent cosmesis by trained nursing assessment. At 3 years, the percentage was 77%, or an absolute change of 7%.⁶² In the study proposed here, a subset of patients may receive a boost to the lumpectomy cavity which has been associated with a slightly higher risk of fibrosis and adverse cosmesis.^{63,64} Therefore, the sample size proposed for arms 1-2 is based on an assumed value of a 10% complication rate in the control arm. The rate of grade 3 or higher late toxicity in this population is expected to be $\leq 1\%$ (Whelan ASCO 2011). Since the local failure rate and death rate at 2-years in the UK start B trial²⁴ was less than 3% we assume that an additional 10% to account for patients lost to follow, failures, deaths and others should be adequate (Total enrollment of 110 patients).

16.5 Study Decision Rule and Operating Characteristics

The primary endpoint for this trial is the 24-month complication rate. Complications will be defined as at least one of the following events: 1) grade 3 or higher late adverse event OR 2) deterioration of cosmesis from excellent/good to fair/poor or from fair to poor (using the [Harvard/NSABP/RTOG Cosmesis Scale](#))

The proposed analysis would be to compute the difference in the 24-month complication rate between the experimental arm and the control arm. A one-sided 90% confidence interval (with the upper bound of the interval) was computed by assuming a 10% complication rate in the control arm and a 15% “non-inferiority margin” of the difference (i.e. the maximum the difference can be between the experimental arm and control arm, the largest difference we’re willing to accept). The decision rule would be of the following:

- *Upper bound of the one-sided confidence interval (CI) for the difference (experimental arm 24-month complication rate minus control arm 24-month complication rate) lies above 15% then **recommend that the experimental arm is not investigated further**. The 24-month complication rate of the experimental arm is unacceptably high.*
- *Upper bound of the one-sided confidence interval (CI) for the difference (experimental arm 24-month complication rate minus control arm 24-month complication rate) is less than 15% then **recommend that the experimental arm undergo further investigation**. The 24-month complication rate of the experimental arm is potentially acceptable.*

With 100 evaluable patients, this study has 80% power with a 1-sided alpha of 0.05 to test a null hypothesis that the control arm complication rate is 10% and experimental arm control rate is 25% versus an alternate hypothesis that the complication rate in both arms is 10%. Sample size was computed using PASS v.15 software.

Other considerations: Adverse events, quality/duration of response, and patterns of treatment failure observed in this study, as well as scientific discoveries or changes in standard care will be taken into account in any decision to terminate the study.

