2.0 Goals

2.1 Primary Objectives

2.1.1 To determine the 24-month complication rate of 5 fraction whole radiotherapy +/- concurrent boost as compared to 15 fraction radiotherapy +/- sequential boost. Complications will be defined as one or more of the following events: 1) grade 3 or higher late adverse event, 2) deterioration of cosmesis from excellent/good to fair/poor or from fair to poor.

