10.22 Assessment of Attribution

Only G4 or G5 adverse events will require an attribution. Any change in the grade of an adverse event within the list of monitored AEs will be recorded and considered to be related to treatment. Any new adverse not listed occurring within the Radiated area or in close proximity will be graded and attribution defined by the study PI.

Events determined to be possibly, probably or definitely attributed to a medical treatment suggest there is evidence to indicate a causal relationship between the treatment and the adverse event.

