16.0 Statistical Considerations and Methodology

- 16.1 Overview: This is an open label phase III randomized controlled trial to determine the safety of 5 fraction vs 15 fraction radiotherapy after breast conserving surgery. The goal is to determine whether the difference in 24-month complication rates between the experimental arm and the control arm is acceptable. Of interest is whether the experimental arm results in an unacceptable increase in the 24-month complication rate. If it does not, then the experimental arm will be recommended for further study. If the 24-month complication rate is found to be unacceptable, then the recommendation would be to do no further studies of the experimental arm.

- 16.2 Primary and Secondary Endpoints

16.21 Primary Endpoint: The 24-month complication rate, defined as the percentage of women evaluable at 24 months who develop one or more of the following events:

- 1) grade 3 or higher late adverse event OR
- 2) deterioration of cosmesis from excellent/good to fair/poor or from fair to poor at the 24-month evaluation (using the Harvard/NSABP/RTOG Cosmesis Scale)

16.22 Secondary Endpoints:

16.221 Acute and late adverse events including grade ≥ 2 pneumonitis.

16.223 Locoregional control, invasive disease-free, distant recurrence, disease-free survival, cause-specific survival, overall survival.

The following definitions are used for the secondary endpoints of interest:

- *Acute adverse events*: any adverse event, regardless of attribution, that occurs in the first 90 days post-RT.
- *Late adverse events* (up to 5 years post RT): any adverse event that occurred after the first 90 days post-RT and up to 5 years post-RT.
- *Ipsilateral breast tumor recurrence (IBTR)*: this is defined as local recurrence from trial registration as a first event at 5 years. IBTR is defined as both invasive and non-invasive breast cancer involving the same breast parenchyma as the original tumor.
- *Regional recurrence*: invasive breast cancer in the axilla, regional lymph nodes, chest wall, and skin of the ipsilateral breast at 5 years.
- *Distant recurrence*: metastatic cancer that has either been biopsy confirmed or clinically diagnosed as recurrent invasive breast cancer at 5 years.

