16.6 Analysis Plan

The analysis for this trial will commence at the planned time points and at the time the patients have become evaluable for the primary endpoint.

16.6.1 Primary Analysis: The primary analysis will be to estimate the difference in the complication rate (adverse cosmesis and grade 3+ toxicities) which is defined as the 24-month complication rate in experimental arm minus that in the control arm. All patients meeting the eligibility criteria who have signed a consent form and started treatment will be in the primary analysis. The complication rate will include all women evaluable at 24 months. Those who have recurrent disease or die before 24 months will not be included in this calculation. We expect that <3% of patients will not be found eligible based on failure or death.²⁴ The complication rate will be estimated using a binomial estimator in both experimental arm

and control arm, and a one-sided 90% confidence interval of the difference will be computed with normal approximation. As mentioned above, the following decisions will be made based on the 90% CI:

- ***The upper bound of the 1-sided 90% CI of the difference lies below 15%:*** The experimental arm regimen is acceptable.
- ***The upper bound of the 1-sided 90% CI of the difference lies above 15%:*** The experimental arm regimen is unacceptable.

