16.62 Secondary Analyses

16.621 *Acute adverse events:* All patients who were registered to the study and started treatment will be included in the acute adverse event analysis. An acute adverse event is an AE, regardless of attribution, that occurs up to 90 days post-RT. The maximum grade for each type of acute AE will be recorded for each patient. Data will be summarized as frequencies and relative frequencies by treatment arm. Additionally, the relationship of the adverse event(s) to the study treatment will be taken into consideration. Rates will be compared between arms using chi-squared tests.

16.622 *Late adverse events:* All patients who were registered to the study and started treatment will be included in the late adverse event analysis. A late adverse event is an AE, regardless of attribution, that appears or persists after 90 days post-RT and up to 5 years post-RT. The maximum grade for each type of late AE will be recorded for each patient. Data will be summarized as frequencies and relative frequencies by treatment arm. Additionally, the relationship of the adverse event(s) to the study treatment will be taken into consideration. Rates will be compared between arms using chi-squared tests.

16.623 *Locoregional control:* The cumulative incidence of locoregional recurrence will be estimated using a competing risks method (Gooley et al.) by treatment arm. The competing risks will be distant breast cancer recurrence and death. Comparison between arms will employ Fine-Gray regression.

16.624 *Invasive disease-free survival:* i-DFS is defined as the time from registration until the time of invasive disease recurrence (not including DCIS) or death due to any cause. The i-DFS will be estimated with a Kaplan-Meier estimator and curve by treatment arm. Estimates will be given for specific time points along with 95% CIs. Comparison between arms will employ a log-rank test.

16.625 *Disease-free survival:* DFS is defined as the time from registration until the time of disease recurrence or death due to any cause. The DFS will be estimated with a Kaplan-Meier estimator and curve by treatment arm. Estimates will be given for specific time points along with 95% CIs. Comparison between arms will employ a log-rank test.

16.626 *Cause specific survival:* The CSS will be estimated with a Kaplan-Meier estimator and curve by treatment arm. Estimates will be given for specific time

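### Does the primary endpoint need to say whether a grade 3 or higher late adverse event counts whatever its cause?

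*Combined protocol and SAP*

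**What the plan says.** The adverse-event half of the composite appears three times. Section 16.5 has "Complications will be defined as at least one of the following events: 1) grade 3 or higher late adverse event". Section 2.1.1 gives it as "grade 3 or higher late adverse event, 2) deterioration of cosmesis from excellent/good to fair/poor or from fair to poor", and 16.21 repeats it in nearly the same words. None of the three mentions cause.

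A late adverse event is defined in two places, both written for secondary endpoints. The list in 16.22 has "any adverse event that occurred after the first 90 days post-RT and up to 5 years post-RT". Section 16.622 has "A late adverse event is an AE, regardless of attribution, that appears or persists after 90 days post-RT and up to 5 years post-RT", and adds: "Additionally, the relationship of the adverse event(s) to the study treatment will be taken into consideration".

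Two other places use a different word. Section 16.6.1 sets out to "estimate the difference in the complication rate (adverse cosmesis and grade 3+ toxicities", and 16.4 says: "The rate of grade 3 or higher late toxicity in this population is expected to be" at most 1%.

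On attribution, 10.22 opens with "Only G4 or G5 adverse events will require an attribution". It goes on to treat any grade change in a monitored event as related, and to have the principal investigator attribute new unlisted events in or near the irradiated area. Section 10.5 requires grade 3, 4 and 5 events outside the 10.4 list to be submitted whatever their cause.

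**The concern.** On a first reading the plan seems to point two ways. The definitions in 16.22 and 16.622 suggest events of any cause, but they are headed as secondary. The planning rate in 16.4 and the wording of 16.6.1 speak of toxicity, which suggests treatment-related events only. If related events were meant, the first sentence of 10.22 suggests that attribution of grade 3 events might not be on file.

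The decision rule is a fixed cut-off applied to about 50 women per arm in an open-label trial. If the counting rule really were open, it could be settled after results by arm were known, and a single unrelated grade 3 event could turn an acceptable verdict into an unacceptable one. An any-cause count would also raise the event rate in both arms above the 10% assumed for sizing, which costs power.

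**Working it through.** **Reading the definitions together**

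- The endpoint uses the term late adverse event. Both definitions of that term cover any event, and 16.622 rules out an attribution filter explicitly. No other section gives the term a narrower meaning.
- Section 16.72 counts only events at least possibly related to treatment, and says so. The primary endpoint carries no such qualifier.
- Toxicity is not a separate concept in this plan: objective 2.21 speaks of acute and late toxicity, and 16.221 turns the same item into acute and late adverse events.
- Any-cause counting needs no attribution, so 10.22 does not limit it. The required events come in through 10.4 and 10.5.
- Even under a related-only reading, 10.22 settles listed events and unlisted events in or near the field. What remains is unlisted grade 3 events away from the breast.

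**The plan's own power figure**

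Inputs from 16.4 and 16.5: 50 evaluable per arm, 10% in both arms, margin 15 points, one-sided 0.05.

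- SE = sqrt(2 × 0.10 × 0.90 / 50) = 0.060
- Power = Φ(0.15/0.060 − 1.645) = Φ(0.855) = 80.4%, which reproduces the stated 80%.
- With the one-sided 90% bound that 16.6.1 uses for the decision: Φ(2.5 − 1.2816) = Φ(1.218) = 88.8%.

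**One-woman reversal**

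Upper bound = d + 1.2816 × sqrt(pe(1−pe)/50 + pc(1−pc)/50).

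- 8/50 against 5/50: 0.06 + 1.2816 × 0.0670 = 14.6%, acceptable.
- 9/50 against 5/50: 0.08 + 1.2816 × 0.0689 = 16.8%, unacceptable.

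A pair like this exists for every control count from 0 to 10. It is a property of any fixed cut-off at this sample size and does not measure the ambiguity. The chance of landing on the last passing count is about 8.6% when both true rates are 10%, and 13.5% at 15% against 10%.

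**Cost of the any-cause reading**

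Let b be the rate of unrelated grade 3 or higher late events, equal in the arms and independent of complications. The documents give no value, so b is an assumption shown over a range. The rate in each arm becomes p′ = 0.10 + 0.90b, and power is Φ(0.15/sqrt(2p′(1−p′)/50) − z).

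| b | p′ | Power, 90% bound (z = 1.2816) | Power, one-sided 0.05 (z = 1.645) |
|---|---|---|---|
| 0 | 10.0% | 88.8% | 80.4% |
| 1% | 10.9% | 87.0% | 77.7% |
| 2% | 11.8% | 85.2% | 75.2% |
| 5% | 14.5% | 80.2% | 68.6% |
| 10% | 19.0% | 73.6% | 60.5% |

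With the 90% bound, power reaches 80% at b = 5.13%.

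**Dilution**

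A true excess of 15 points shrinks to 15 × (1 − b): 14.7, 14.25 and 13.5 points at b = 2%, 5% and 10%. False acceptance at 25% against 10% with the 90% bound is Φ((0.15 − 0.15(1−b))/SE − 1.2816). It rises from 10.0% to 10.7%, 11.7% and 13.4%.

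**How often the two readings disagree**

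Simulated trials with 50 per arm, related events at 10% in both arms and the 16.6.1 rule give opposite verdicts in 4.2%, 7.1%, 13.3% and 20.3% of trials at b = 1%, 2%, 5% and 10%. At 2%, 5% and 10%, 5.4, 11.2 and 17.6 of those percentage points are cases where related-only would accept and any-cause would not.

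**The case for a change.** The best argument for a change is that the two definitions belong to secondary analyses with a different population and a five-year window, so they do not formally govern the primary endpoint. Section 16.622 also weakens its own rule by saying that relationship will be considered, without saying how. The 1% planning figure makes no visible allowance for unrelated events. In a small open-label trial, a go/no-go rule should leave nothing to choose afterwards, and a clarifying sentence would be cheap.

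Part of this stands. The primary text is silent on cause, and if unrelated grade 3 events were as common as 10%, power under the stated bound would be 73.6%.

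The rest is weaker than it looks. A term defined twice in the same chapter, both times without a causal filter, keeps that meaning unless the plan says otherwise. The planning figure comes from a cited report, and the documents do not say whether it counted related or all events, so it cannot show that only the toxicity reading fits. Section 16.6.1 drops women who recur or die before 24 months, which removes some unrelated events. The stopping rule in 16.72 covers the first 90 days, so any friction with 10.22 over grade 3 attribution there does not reach a late-event endpoint.

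The main alternative, counting only events on the 10.4 list, is a trade-off and not a clear improvement. It would leave unlisted local grade 3 harms out of the primary analysis of a trial whose stated purpose is safety. It would also need the site of pain, and 10.4 lists pain only as a general item, with no site shown.

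**Conclusion.** No change is needed. Read as a whole, the plan counts grade 3 or higher late events of any cause, and an analyst following it would reach that reading without inventing a rule. That count compares the randomised arms without a judgement about cause, which suits an open-label design. The gap left by the wording is narrow: mainly unlisted grade 3 or higher events away from the irradiated area.

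The size of the effect rests on an unrelated-event rate that the documents do not give, assumed equal between arms and independent of complications. Under the 90% bound in 16.6.1, power is 87.0% at a 1% rate, 80.2% at 5% and 73.6% at 10%. False acceptance moves from 10.0% to 11.7% at 5%. The larger power losses appear only with one-sided 0.05. The difference between that level in the 16.5 power statement and the 90% interval in the decision rule is a separate matter and does not bear on this one. The conclusion would weaken only if unrelated events were well above 5%, and nothing in the documents indicates that.

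### An upper bound above 15% shows only that a 15-point increase was not excluded, but the plan concludes from it that the 5-fraction complication rate is unacceptably high

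*Combined protocol and SAP*

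**What the plan says.** Section 16.5 computes the difference in 24-month complication rate, experimental minus control, with a one-sided 90% confidence interval and a 15-point non-inferiority margin. It allows two outcomes.

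- **Upper bound above 15%.** The action is to "recommend that the experimental arm is not investigated further". The conclusion attached is: "The 24-month complication rate of the experimental arm is unacceptably high".
- **Upper bound below 15%.** The arm goes on to further investigation. The conclusion is: "The 24-month complication rate of the experimental arm is potentially acceptable".

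Section 16.6.1 applies the same rule and specifies the normal approximation. Its conclusions are shorter: "The experimental arm regimen is unacceptable" and "The experimental arm regimen is acceptable". Section 16.1 frames the unfavourable result the same way: "If the 24-month complication rate is found to be unacceptable, then the recommendation would be to do no further studies of the experimental arm".

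The hypotheses in 16.5 are a null of 10% in the control arm against 25% in the experimental arm, and an alternative of 10% in both. No section sets a condition on the lower bound or provides for a result that does not settle the question.

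**The concern.** Under these hypotheses, an upper bound above 15% is failure to reject the null that the experimental arm is 15 points worse. It is not evidence that the null is true. Sections 16.5 and 16.6.1 nevertheless prespecify a statement of fact about the experimental rate for that result. A regimen with the same true rate as control, or with an increase well inside the margin, would be recorded as having an unacceptable complication rate in a calculable share of trials.

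The favourable side has a smaller problem. The same event is *potentially acceptable* in 16.5 and plainly *acceptable* in 16.6.1. The second says more than that an increase of 15 points or more was excluded.

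**Working it through.** **Inputs.** 50 evaluable women per arm (16.4); 10% control rate, 15-point margin and one-sided 90% interval (16.5); normal approximation (16.6.1). The true rates of 15%/15% and 10%/15% are assumed sensitivity cases.

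**The plan's own figure.** Section 16.5 states: "With 100 evaluable patients, this study has 80% power with a 1-sided alpha of 0.05". With 10% in both arms the standard error is sqrt(2 × 0.10 × 0.90 / 50) = sqrt(0.18/50) = 0.06. Power is Φ(0.15/0.06 − 1.645) = Φ(0.855) = 80.4%, so the stated figure is reproduced. With the 90% bound that 16.6.1 uses for the decision, power is Φ(2.5 − 1.282) = 88.8%, so the unfavourable conclusion has an approximate probability of 11.2% when the arms are identical at 10%.

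**Exact frequency of the unfavourable conclusion.** All 51 × 51 outcomes were enumerated with binomial weights. For each, with d the observed difference and s = sqrt[c(1−c)/50 + t(1−t)/50], where c and t are the observed control and experimental rates, the limits are d ± 1.282 s. The rule fires when the upper limit reaches 15%.

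| True rates, control / experimental | Labelled unacceptable (90% bound) | Lower 90% limit above 15% | Labelled unacceptable (95% bound) |
|---|---|---|---|
| 10% / 10% | 10.9% | 0.01% | 19.4% |
| 15% / 15% | 20.7% | 0.04% | 31.2% |
| 10% / 15% | 39.8% | 0.3% | 53.3% |
| 10% / 25% | 89.5% | 10.2% | 94.2% |

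The last column uses the bound that matches the one-sided 0.05 used for sizing. The plan decides on the 90% bound, so the second column is the operative one.

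**Where the label starts.** Take 5/50 (10%) in the control arm.

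- 8/50 experimental: d = 6 points, upper limit 14.6%, favourable.
- 9/50: d = 8 points; s = sqrt(0.0018 + 0.002952) = 0.0689; limits 8 ± 1.282 × 6.89, which is -0.8% to 16.8%. Labelled unacceptably high.
- 17/50: d = 24 points; s = sqrt(0.0018 + 0.004488) = 0.0793; lower limit 24 − 10.2 = 13.8%, still below 15%.
- 18/50: d = 26 points; lower limit 15.7%, the first result to show an increase beyond the margin at this level.

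So 9 to 17 experimental events out of 50 carry the label although none of them shows an increase beyond 15 points.

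**The case against.** The strongest reply is that this is a go/no-go rule. Section 16.1 presents the output as a recommendation for or against further study, and 16.5 defines 15 points as the largest difference that would be accepted. Declining to continue when non-inferiority has not been shown is legitimate, and the 10.9% at the design rates is ordinary type II error, lower than the 20% implied by the stated power. All of that stands. The action is sound. The sentence about the rate that accompanies it is not.

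Some stronger readings are tempting, but the documents do not support them.

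- *The trial would publish an inconclusive result as proof of harm.* No section fixes publication wording. Section 16.8 commits to registry reporting of the endpoints, and section 20.0 covers only responsibility and approval for publication. What is fixed is the conclusion in 16.5 and 16.6.1.
- *Most flagged results are compatible with no increase at all.* This depends on the confidence level. With both rates at 10%, 74% of flagged results have a two-sided 95% interval that includes zero. At the plan's one-sided 90% level, however, 8.0 of the 10.9 percentage points have a lower limit above zero, and only about 26% of flagged results do not (2.8/10.9). What almost all of them leave open is whether the increase exceeds 15 points.
- *The rule wrongly accepts a harmful regimen.* At the FAST 30 Gy and 50 Gy rates cited in section 1.3 (17.3% and 9.5%), the rule would be favourable in about 43% of trials. That difference is 7.8 points, inside the margin, so a favourable result there is not an error. The FAST endpoint and schedule also differ from this trial's.

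On the two favourable wordings, 16.6.1 does refer back to the earlier rule, so this is a minor inconsistency. It still needs reconciling.

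**Conclusion.** The concern holds as a wording error in the prespecified primary conclusion. An upper bound above 15% supports *non-inferiority not shown*. It does not support *unacceptably high*. At the plan's 90% bound the unsupported statement is made, with the true difference inside the margin, in 10.9% of trials at 10%/10%, 20.7% at 15%/15% and 39.8% at 10%/15%. These figures assume 50 evaluable women per arm, independent binomial outcomes and the planned Wald limits. A 95% bound would raise them to 19.4%, 31.2% and 53.3%. The mismatch between the sizing alpha and the interval level is a separate matter that changes how often the mislabelling occurs, not whether it exists. When the true increase really is 15 points or more, the label would be true, but the rule would not have shown it. The go/no-go decision, endpoint and sample size are not in question.

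**What to change.** Keep the recommendation in each branch and replace the conclusion sentences.

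- **Upper bound below 15%:** an increase of 15 points or more is excluded; potentially acceptable; recommended for further investigation. Use the same words in 16.5 and 16.6.1.
- **Upper bound at or above 15%:** non-inferiority not shown; not recommended for further investigation. This also assigns a bound of exactly 15%, which neither section covers now.
- **Reserve unacceptably high** for a lower bound above 15% at the same stated confidence level.
- **Section 16.1:** change the phrase about a rate found to be unacceptable so that it matches.
- **Reporting:** give the point estimate with both limits and state the level. Two one-sided 90% limits form a two-sided 80% interval, and the report should say so.

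A middle category of *higher than control*, triggered by a lower bound above zero, is not advised at the 90% level. It would be declared in 8.0% of trials with identical 10% arms, and it tests zero instead of the 15-point margin that defines acceptability here.

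The cost is wording in three subsections, with no change to data, patients, sample size or action. It should be made before outcomes by arm are known, because rewording afterwards would look driven by the result.

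### The acceptance rule uses a one-sided 90% bound (alpha 0.10), but the sample size and power are stated for one-sided alpha 0.05, so as written the false-acceptance risk is about twice the stated 5%

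*Combined protocol and SAP*

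**What the plan says.** The plan gives two error levels for one decision.

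- **Design level.** In 16.5, "this study has 80% power with a 1-sided alpha of 0.05 to test a null hypothesis that the control arm complication rate is 10"% in the control arm and 25% in the experimental arm, against an alternative of 10% in both arms. Section 16.4 sets 50 evaluable women per arm, "based on an assumed value of a 10% complication rate in the control arm".
- **Level of the rule in 16.5.** "A one-sided 90% confidence interval (with the upper bound of the interval) was computed by assuming a 10% complication rate in the control arm". The margin there is 15 percentage points. The two decision bullets that follow refer to a one-sided interval and repeat no level.
- **Level of the rule in 16.6.1.** "a one-sided 90% confidence interval of the difference will be computed with normal approximation". The regimen is acceptable if "The upper bound of the 1-sided 90% CI of the difference lies below 15"% and unacceptable if the bound lies above it.

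The one-sided 90% wording occurs four times: once in 16.5, once in the text of 16.6.1 and once in each 16.6.1 decision bullet. One further mention in 16.6.1 refers to the 90% CI without giving a side. A two-sided interval is mentioned nowhere for this analysis.

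**The concern.** Declaring non-inferiority when a one-sided 100(1 − α)% upper bound falls below the margin is a test at one-sided level α. A one-sided 90% bound therefore carries a nominal 10% risk of accepting a regimen whose true excess equals the margin. The power sentence puts that risk at 5%.

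This is the only decision rule for the primary safety question, and the discrepancy favours accepting the experimental arm. An analyst who follows 16.6.1 literally will use z = 1.282; one who follows the power statement will use z = 1.645. The trial is open label, so if the choice stays open until results by arm are visible, it could be made knowing which level gives which verdict.

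**Working it through.** **Inputs, all from 16.4 to 16.6.1.** Control rate 10%. Experimental rate 25% under the null; 16.5 words this as "experimental arm control rate is 25"%, which I read as the complication rate. Both rates 10% under the alternative. Margin 0.15. Evaluable n = 50 per arm. Normal approximation. z(0.95) = 1.645, z(0.90) = 1.282, z(0.80) = 0.842.

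**1. Reproduce the plan's figures at alpha 0.05 (unpooled variance).**

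- SE = √(2 × 0.10 × 0.90 / 50) = 0.060
- Power = Φ(0.15/0.060 − 1.645) = Φ(0.855) = 80.4%
- n per arm = 2 × 0.10 × 0.90 × (1.645 + 0.842)² / 0.15² = 49.5, rounded up to 50

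This matches the stated 100 evaluable women and 80% power.

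**2. Repeat at the level of the written rule, alpha 0.10.**

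- Power at 50 per arm = Φ(0.15/0.060 − 1.282) = Φ(1.218) = 88.8%
- n per arm for 80% power = 0.18 × (1.282 + 0.842)² / 0.15² = 36.1, rounded up to 37 (74 evaluable in total)

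With this formula, the stated sample size and power belong to alpha 0.05 and not to the 90% bound.

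**3. Exact behaviour of the rule.** For every pair of event counts at 50 per arm, I took the binomial probability and applied the rule: accept if d + z × √[p₁(1 − p₁)/50 + p₀(1 − p₀)/50] < 0.15, where p₁ and p₀ are the observed experimental and control rates and d = p₁ − p₀.

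| True rates (experimental vs control) | One-sided 90% bound | One-sided 95% bound |
|---|---|---|
| 25% vs 10%: false acceptance | 10.5% | 5.8% |
| 10% vs 10%: power | 89.1% | 80.6% |

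For control rates of 5% to 20% with a true 15-point excess, false acceptance is 10.1% to 12.1% with the 90% bound and 5.2% to 6.4% with the 95% bound. The finding does not depend on the 10% control rate.

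**4. A result that changes verdict.** Take 5/50 control events (the assumed 10%) and 8/50 experimental events.

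- d = 0.16 − 0.10 = 0.06
- SE = √(0.16 × 0.84/50 + 0.10 × 0.90/50) = √0.004488 = 0.0670
- 90% bound: 0.06 + 1.282 × 0.0670 = 14.6%, acceptable
- 95% bound: 0.06 + 1.645 × 0.0670 = 17.0%, unacceptable

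With 5/50 in the control arm, the 90% bound accepts up to 8 experimental events and the 95% bound up to 7.

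**The case against.** The strongest reply is that the authors meant the upper limit of a two-sided 90% interval, which is a one-sided 95% bound. The rule would then run at a nominal 5% and only the label would be wrong. This is plausible, because the sample size fits it and one mention of the 90% CI gives no side. It remains an inference: the one-sided label is written four times in two sections.

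Second, the match to alpha 0.05 depends on the variance formula. Section 16.5 names the software but not the test statistic. With the variance taken under the null (0.10 × 0.90 + 0.25 × 0.75 = 0.2775), alpha 0.10 gives 48 per arm and 81.8% power at 50, while alpha 0.05 needs 67 per arm. That variant does not give 50 and contradicts the stated alpha. The unpooled formula gives 50 and is consistent with the normal approximation in 16.6.1. A continuity correction to the 90% bound would lower exact false acceptance to 6.7%, with 81.6% power, but the plan does not mention one.

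Third, a positive result leads only to further study (16.1, 16.5), and a 10% one-sided error could be a deliberate choice for that purpose. This stands as far as it goes: the fault is the mismatch, not the 90% level itself. But 16.6.1 says simply that the regimen is acceptable, the trial is labelled phase III, and the stated alpha is 0.05.

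Power is not overstated. Under the written rule it is higher than claimed, so the cost falls entirely on false acceptance.

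**Conclusion.** The concern holds. As written, the primary decision rule has a nominal one-sided type I error of 10% against a stated 5%. The exact figure is 10.5%, about 2.1 times the stated level (10.5/5) and 1.8 times the exact error of the aligned rule (10.5/5.8). This assumes 50 evaluable women per arm, a 10% control rate, a true difference equal to the 15-point margin, and the uncorrected normal-approximation interval with unpooled variance. If a two-sided 90% interval was intended, the fault is in the wording alone, but that wording controls the primary verdict and can reverse it. It must be corrected before the analysis.

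**What to change.** In 16.5 and 16.6.1, replace each of the four one-sided 90% statements with: one-sided 95% upper confidence bound, equal to the upper limit of the two-sided 90% confidence interval. Amend the unsided mention of the 90% CI in 16.6.1 in the same way, and state the level in the 16.5 decision bullets. The rule then agrees with alpha 0.05, 80% power and 100 evaluable women. The 5% is nominal: with the planned interval the exact figure is 5.8% at 25% vs 10%, which the plan could note.

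If the sponsor does intend the one-sided 90% bound, keep it and restate alpha as 0.10 and power as about 89% at 50 per arm, with a reason for accepting a 10% error on the primary safety question.

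Either change is wording in two sections and needs no extra patients. It should be made before outcomes are compared by arm, and the variance formula used in the sample-size software should be recorded at the same time.
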